7.8.1 Analysis of Primary Efficacy Endpoint

The primary efficacy endpoint is percent change from baseline in PVR immediately before PEA at Visit 2.

The null hypothesis is that there is no difference between the treatment groups in percent change from baseline in PVR immediately before PEA at Visit 2, and the alternative is that the difference is not zero.

The difference in the percent change from baseline in PVR immediately before PEA at Visit 2 between riociguat and placebo will be tested using the 2-sample Wilcoxon rank-sum test. If the normality of the residuals can hold, as a supportive analysis, analysis of covariance with baseline value as the covariate will be employed to test the null hypothesis.

To check the effect of missing values on the robustness of the primary analysis, the primary analysis will be repeated using the baseline observation carried forward approach for missing PVR values immediately before PEA at Visit 2.

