4.3.3. Per Protocol Set (PPS)

The PPS will consist of all ITT patients who fulfil all inclusion/exclusion criteria, have at least 80% overall dose compliance with study drug, have not taken any prohibited medication, have no significant protocol deviations, have valid PVR assessments at baseline (from patient history) and Visit 2, and undergo PEA as planned. All analyses using the PPS will group patients according to treatment actually received. A blind review of data will identify which patients will be included in the PPS.

The PPS will be used in the primary and secondary efficacy analyses as supportive analyses.

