8.1. Primary Efficacy Endpoint

As defined in Section 3.2.1, the primary efficacy endpoint is percent change from baseline in PVR immediately before PEA at Visit 2. The PVR assessment from Visit 2 needs to be within 7 days prior to PEA. Assessments out of the time frame will be considered invalid and be treated as missing. In the case of patients who do not undergo PEA, the PVR at Visit 2 will be treated as missing.

The null hypothesis is that there is no difference between the treatment groups in percent change from baseline in PVR immediately before PEA at Visit 2, and the alternative is that the difference is not zero. The primary efficacy analyses will be conducted using the ITT set. Similar analysis will be repeated for the PPS as the supportive analysis.

The difference in the percent change from baseline in PVR immediately before PEA at Visit 2 between riociguat and placebo will be tested using the 2-sample Wilcoxon rank-sum test.

Analysis of covariance (ANCOVA) with baseline value as the covariate will be employed to test the null hypothesis as a supportive analysis. Residuals for percent change from baseline in PVR will be generated by using PROC GLM procedure with baseline value as the covariate. A quantile-quantile (Q-Q) plot of residuals with p-value from Shapiro-Wilk test will be presented to test the normality of the residuals.

To check the effect of missing values on the robustness of the primary analysis, the primary analysis will be repeated using the baseline observation carried forward approach for missing PVR values immediately before PEA at Visit 2.

The PVR will be measured at pre-PEA visit (Visit 2) and at the 6-month follow-up visit (Visit 4). Observed values, changes from baseline and percent change from baseline will be provided for PVR using descriptive statistics by treatment group and scheduled visit.

Boxplot will be used to present the percent change from baseline in PVR by treatment group and scheduled visit. The upper (lower) edge of the box represents the 75th (25th) percentile. A horizontal line in the box interior represents the median. Above the box a vertical line indicates the region from the 3rd quartile to the 95% percentile; below the box a vertical line indicates the region from the 1st quartile to the 5% percentile. Values outside the whiskers are displayed by a distinct marker.

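### The only missing-data check on the primary endpoint carries baseline forward for every reason, so it cannot show whether the PVR result depends on deaths or deterioration before PEA

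*SAP*

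**What the plan says.** The primary endpoint is percent change in PVR from baseline to the catheterisation just before PEA. The two arms "will be tested using the 2-sample Wilcoxon rank-sum test" (SAP 8.1), and the set is stated: "The primary efficacy analyses will be conducted using the ITT set". No imputation is given for this main test, so it runs on available values.

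A Visit 2 value can be missing in more ways than not being measured. On timing: "Assessments out of the time frame will be considered invalid and be treated as missing". On surgery: "In the case of patients who do not undergo PEA, the PVR at Visit 2 will be treated as missing". The second rule covers every death before PEA.

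The one analysis aimed at missing values is in SAP 8.1: "the primary analysis will be repeated using the baseline observation carried forward approach for missing PVR values immediately before PEA at Visit 2". Protocol 7.8.1 has the same rule. Neither document splits it by reason.

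Two supportive analyses are also planned. The ANCOVA is given no handling of missing values. The per-protocol set is limited to patients who "have valid PVR assessments at baseline (from patient history) and Visit 2, and undergo PEA as planned" (SAP 4.3.3), so it leaves out the patients in question.

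**The concern.** A robustness check should ask whether the result survives a plausible but unfavourable account of the missing values. Here the unfavourable account is that some patients have no pre-operative PVR because they died or became too ill to reach surgery. Scoring them 0% treats them as stable.

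If such losses were more frequent on riociguat, the available-case test would ignore them and the carried-forward test would rank them like ordinary placebo patients. Both could still favour riociguat. If they were more frequent on placebo, the carried-forward run would understate the benefit. In neither direction does the check respond to why the value is missing.

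**Working it through.** **Inputs from the documents.** 88 randomised 1:1, so 44 per arm (SAP 4.1). Target of 80 completers with 10% dropout to Visit 4 (Protocol 4.3.3). Entry PVR above 800 (Protocol 4.1.1). Pivotal-study PVR change of −226 on riociguat and +23 on placebo (Protocol 3.1.1). Two-sided 5% tests (SAP 4). No power or SD is stated.

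**The plan's own figure.** 80 × 1.10 = 88, which matches. (80 / 0.90 = 88.9, or 89, is the other convention.) The whole-study allowance for loss is 88 − 80 = 8 patients.

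**Where a 0% score falls.** Carried forward, percent change = 100 × (baseline − baseline) / baseline = 0. Expected arm means, for assumed baselines of 800 to 1200:
- placebo: 23/1200 = +1.9% to 23/800 = +2.9%
- riociguat: −226/1200 = −18.8% to −226/800 = −28.2%

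The percentile of 0% in an arm is Φ((0 − mean)/SD). With an assumed SD of 15% to 40%:
- placebo: Φ(−2.9/15) = 0.42 to Φ(−1.9/40) = 0.48
- riociguat: Φ(18.8/40) = 0.68 to Φ(28.2/15) = 0.97

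So 0% is poor relative to riociguat responders, which is how the run dilutes a benefit, but ordinary relative to placebo.

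**What the check can detect.** With no drug effect and 8 v 0 patients lost (riociguat v placebo), the chance of a significant result against riociguat is about 2% with carried-forward baseline, which is the chance level of 2.5% or just below it. Worst rank gives about 28%.

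**Effect on a positive result.** Simulated trials, 44 per arm. Visit 2 / baseline ratio = m × exp(s × Z), with Z standard normal, m the arm's median ratio and s the log-SD. Placebo m is 1.02 to 1.03. The lost patients are left out (available case), set to 0% (carried forward), or given the tied worst rank. Chance of p < 0.05 favouring riociguat:

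| Riociguat m | Log-SD | Lost (riociguat v placebo) | Available case | Carried forward | Worst rank |
|---|---|---|---|---|---|
| 0.82 | 0.30 | 3 v 1 | 88% | 87% | 75% |
| 0.82 | 0.30 | 4 v 2 | 88% | 85% | 70% |
| 0.82 | 0.30 | 6 v 2 | 89% | 84% | 49% |
| 0.77 | 0.30 | 6 v 2 | 98% | 96% | 79% |
| 0.82 | 0.20 | 6 v 2 | 100% | 99% | 92% |
| 0.72 | 0.30 | 6 v 2 | 100% | 100% | 97% |

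Repeat runs differ by a few points; worst rank in the third row ranged from 45% to 49%. In the other direction (0.82, 0.30, 2 v 6 lost) the figures are about 88%, 90% and 96%.

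The ratios 0.77 and 0.72 correspond to baselines of 1000 and 800 (1 − 226/1000 = 0.774; 1 − 226/800 = 0.7175). A ratio of 0.82 implies 226/0.18 = 1256, a weaker effect than any baseline from 800 to 1200 gives. The log-SD and the loss counts are assumptions.

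**The case against.** **The large gaps need many losses.** The allowance of 8 covers every reason up to Visit 4. The 6 v 2 rows place all 8 before PEA and attribute all of them to death or deterioration, although entry excludes unstable disease needing urgent surgery. This stands: the 3 v 1 and 4 v 2 rows are nearer what the plan expects, and the gap there is 12 to 15 points.

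**Other analyses exist.** A reader might infer that carried-forward baseline is the only robustness analysis of the primary result. It is not: ANCOVA and a per-protocol repeat are planned. It is the only one that addresses missing values.

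**Deterioration is often measured.** A reader might infer that anyone who worsens is scored as unchanged. The documents do not support that. A patient who worsens, even one operated on early, is scored on the measured value if catheterised within 7 days before PEA. The problem is confined to patients with no valid Visit 2 value, including those catheterised but never operated on.

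**Early harm is reported elsewhere.** A reader might infer that the plan hides it. It does not. Withdrawals before PEA are tabulated by arm and reason on the ITT set (SAP 8.2.6), fatal events are summarised and all deaths listed (SAP 9.1.6), and an unblinded board reviews safety (Protocol 6.5). These are descriptive, however, and do not show whether the PVR comparison survives the losses.

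**It is a different question.** The objective concerns PVR, and worst rank combines PVR with survival. The trial is exploratory and unpowered. Both points are fair, and they argue for a sensitivity run rather than a change to the primary analysis.

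**Conclusion.** The concern holds in a limited form. The one missing-data check treats every reason alike and scores death or clinical deterioration before PEA as no change. It can weaken an apparent benefit but cannot show that the benefit depends on such losses.

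The mid-placebo position of a 0% score is stable over the baselines and SDs tried. The practical size is not. The gap between carried-forward baseline and worst rank is 12 to 15 points with 4 to 6 such losses at a ratio of 0.82 and log-SD 0.30, and about 35 points when the whole dropout allowance is used up 6 v 2. At that same loss it is 17 points with a ratio of 0.77, 7 points with log-SD 0.20 and 3 points with a ratio of 0.72. A reader might infer from the 49% figure that worst rank would usually overturn the result; that figure belongs to a weak effect, a wide SD and heavy loss together. This is a cheap and worthwhile improvement, not a flaw that invalidates the primary analysis.

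**What to change.** In SAP 8.1 and Protocol 7.8.1, keep the carried-forward run and add one Wilcoxon sensitivity run on the ITT set:
- Patients with no valid Visit 2 PVR because of death before PEA, or because of withdrawal or no PEA due to clinical deterioration, take the tied worst rank.
- All other missing values, such as a catheterisation outside the window, keep carried-forward baseline.
- Reasons for a missing Visit 2 PVR are tabulated by arm.

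Start from the discontinuation categories in SAP 5.1 (Death, Adverse Event, Progressive Disease) and confirm each reason at the blind data review before unblinding. Those categories record why a patient did not complete the study, not why a Visit 2 PVR is absent, so they will not settle every case. A short written definition of clinical deterioration is needed before the review.

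The cost is SAP and protocol wording, one more rank test and some blinded adjudication. The run answers a PVR-plus-survival question, so it should be labelled as a sensitivity analysis.

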8.2. Secondary Efficacy Endpoint

Secondary efficacy endpoints are defined in Section 3.2.2.

8.2.1. Pulmonary Vascular Resistance (PVR)

The difference in the percent change from baseline in PVR at Visit 4 between riociguat and placebo will be tested using the 2-sample Wilcoxon rank-sum test for the PEA set and the PPS.

PVR assessment at Visit 4 will use the nominal visit information collected in eCRF without considering the time window because PVR status is expected to be stable after PEA.

8.2.2. Composite Clinical Endpoints

Composite clinical endpoints from randomisation to Visit 4 will be tabulated by treatment group containing the number and percentage of patients with an event as well as the number of event for the PEA set and the PPS. The Fisher exact test will be utilised to test the proportion difference along with the Clopper-Pearson exact CI when applicable. For analysis based on the ordinal response of functional class, the row mean score from the Cochran Mantel-Haenszel test will be used to test the response difference between groups.

Composite clinical endpoints include following clinical endpoints:

- All-cause death

All deaths that happen after randomisation until the date of Visit 4, 6 months after the PEA, will be included.

- PH-related hospitalisation

All PH-related hospitalisation except the in-hospital care after PEA from randomisation until 6 months after PEA will be included.

- Need for PAH-targeted therapy

All PAH-targeted therapy from randomisation until 6 months after PEA will be included.

- Functional class unchanged or worse

When comparing the functional class assessment at Visit 1 with the functional class assessment at other visits, the same class will be defined as unchanged, and a higher class will be defined as worse. The worst case after treatment will be used.

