4.3.3 Replacements

A total of 88 patients will be randomly assigned in the study with a target of 80 patients completing the study with an assumption of a 10% dropout rate.

Therefore, drop out for any reason before the last follow-up visit (Visit 4) will be monitored continuously throughout the study, and patients that drop out will be replaced to make a total number of 88 randomised patients. In case of a high initial dropout rate, the DSMB and the sponsor will evaluate the reasons for drop out and decide in mutual agreement on potential extension of further randomisations.

5 Study Drugs

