7.8.2 Analysis of Secondary Efficacy Endpoint

For the secondary endpoint, percent change from baseline in PVR at Visit 4, the same approach as in the primary analysis will be used.

Composite clinical endpoints at 6 months after PEA will be tabulated by treatment group containing the number and percentage of patients with an event as well as the number of event. The Fisher exact test will be utilised to test the proportion difference along with the Clopper-Pearson exact CI when applicable. For analysis based on the ordinal response of functional class, the row mean score from the Cochran-Mantel-Haenszel test will be used to test the response difference between groups.

Circulatory arrest time from perioperative findings will be tabulated by treatment group using the descriptive statistics. An analysis of variance may be employed to compare the mean difference between 2 groups. In case normality assumption cannot hold, the Wilcoxon rank-sum test should be considered.

Surgery-related complications from the perioperative findings will be tabulated by treatment group in a descriptive way, presenting the number and percentage of patients for each symptom.

For surgical evaluation of specimen endpoints, ease of dissection plane and completeness of disease clearance will be tabulated by treatment group containing the number and percentage of patients in each level. The Cochran-Mantel-Haenszel test will be used to test the ordinal response difference between groups if deemed necessary.

Clot and vessel wall friability, measured as more solid than usual, normal, or more friable than usual, will be tabulated by treatment group containing the number and percentage of

patients in each level. The Cochran-Mantel-Haenszel test will be used to test the ordinal response difference between groups if deemed necessary.

All-cause death during the whole study course and withdrawal during the randomised treatment phase will be tabulated by treatment group containing the number and percentage of patients with event. Time to death will be analysed using the Kaplan-Meier method.

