- When frequency counts are presented, the percentage will be suppressed when the count is zero in order to draw attention to the non-zero counts. A row denoted “Missing” will be included in count tabulations where specified on the shells to account for dropouts and missing values. Percentages will be based on the total number of patients in the respective analysis set unless otherwise specified.
- Unless otherwise specified, statistical tests will be 2-sided and performed using a 5% significance level, leading to 95% (2 sided) confidence intervals (CIs). Modelling techniques will be used in an exploratory sense. No adjustments for multiplicity are made.
- Partial dates will be imputed based on the rules specified in Appendix 13.4.
- All laboratory data will be reported by using the International System of Units.
- Unless otherwise specified, the baseline will be defined as the last valid assessment, including assessments from the unscheduled visit, prior to the study drug administration.
- A Visit 2 assessment is considered as valid only when the assessment is completed within 7 days prior to PEA. For assessments at Visit 4, the nominal visit collected in electronic case report form (eCRF) will be used in the analysis. This rule is applicable to all endpoints derived by the visit.
- By-patient listings will be created for each eCRF module for all screened patients. Patients will be identified in the listings by patient number. If data are to be summarised by visit, the visit name collected on the eCRF page will be used.
- All analyses will be conducted using SAS® software Version 9.3 or later (SAS Institute Inc, Cary, North Carolina).

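### The composite is tested only with Fisher's exact test, which is valid but conservative at about 40 per arm; an exact unconditional test would give modestly more power within the same 5% ceiling.

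*SAP*

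**What the plan says.** SAP 8.2.2 (Composite Clinical Endpoints) tabulates patients with an event by arm, "as well as the number of event for the PEA set and the PPS". The comparison is then: "The Fisher exact test will be utilised to test the proportion difference along with the Clopper-Pearson exact CI when applicable". Protocol 7.8.2 names the same test: "The Fisher exact test will be utilised to test the proportion difference".

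The only other test in SAP 8.2.2 concerns one component and not the composite: "For analysis based on the ordinal response of functional class, the row mean score from the Cochran Mantel-Haenszel test will be used".

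SAP Section 4 (General Statistical Considerations) sets the level: "Unless otherwise specified, statistical tests will be 2-sided and performed using a 5% significance level". On numbers, Protocol 4.3.3 has "A total of 88 patients will be randomly assigned in the study with a target of 80 patients completing the study"; the dropout allowance there is 10%, and allocation is 1:1. Neither document gives an expected composite event rate, or a power or achieved size for this test.

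**The concern.** Fisher's test conditions on the total number of events. Few 2x2 tables are possible for a given total, so the attainable p-values are coarse. Averaged over totals, the real rejection rate under no difference falls below the nominal level. In a trial of about 40 per arm the shortfall can be noticeable.

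Boschloo's test uses the Fisher p-value as its statistic but refers it to the unconditional distribution, maximised over the common event rate. It therefore recovers part of the unused error rate without exceeding 5%. At stake is some power to detect a real difference in the composite, in a study whose size was set by feasibility.

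**Working it through.** **1. The plan's own figure.** 80 completers at 10% dropout: 80 x 1.10 = 88, the planned number. Dividing instead gives 80 / 0.90 = 88.9, or 89; and 88 x 0.90 = 79.2. The plan reproduces, and 80 completers at 1:1 is about 40 per arm.

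**2. Inputs.** Two-sided 5% (SAP Section 4); 1:1 allocation; arm sizes near 40. The PEA set and PPS have no stated sizes, so several splits were tried. Event rates are assumptions.

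**3. Formulas.** For x1 of n1 and x2 of n2 events, pF is the two-sided Fisher p-value, summing all tables with the same total that are no more probable than the one observed. With b the binomial probability:

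- Fisher size at common rate π = sum over tables with pF ≤ 0.05 of b(x1; n1, π) b(x2; n2, π).
- Boschloo critical value c = the largest c for which the maximum over π of Pr(pF ≤ c) is at most 0.05.
- Power is the same sum with different rates in the two arms.

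Given the total, Pr(pF ≤ c) is at most c. Averaging over totals keeps it at most c, so Boschloo's p-value is never larger than Fisher's.

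**4. Fisher's true size (%), by common event rate.** Rates above 50% mirror those below.

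| Split | 20% | 30% | 40% | 50% | Boschloo cut-off on pF |
|---|---|---|---|---|---|
| 40/40 | 2.82 | 2.82 | 3.00 | 3.30 | 0.0707 |
| 40/39 | 3.82 | 3.68 | 3.87 | 4.22 | 0.0591 |
| 41/40 | 3.88 | 3.77 | 4.10 | 4.48 | 0.0600 |
| 41/39 | 3.81 | 3.72 | 3.99 | 4.22 | 0.0633 |
| 42/38 | 3.41 | 3.67 | 3.99 | 4.39 | 0.0606 |
| 43/37 | 3.40 | 3.65 | 3.92 | 4.13 | 0.0627 |
| 44/36 | 3.63 | 3.66 | 3.93 | 4.29 | 0.0625 |
| 42/41 | 3.94 | 3.87 | 4.34 | 4.75 | 0.0608 |

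At 40/40 the maximum size of Boschloo's test is 4.77%.

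**5. Power (%), Fisher to Boschloo.** In unequal splits the first rate belongs to the larger arm. By symmetry, 50% v 75% at 40/40 equals 50% v 25%.

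| Rates | 40/40 | 41/40 | 41/39 | 43/37 |
|---|---|---|---|---|
| 10 v 30 | 53.4 to 59.2 | 61.7 to 64.3 | 58.9 to 63.3 | 57.6 to 63.9 |
| 20 v 40 | 40.8 to 47.6 | 47.5 to 51.6 | 43.9 to 49.1 | 45.6 to 48.7 |
| 30 v 50 | 36.8 to 44.1 | 43.1 to 44.0 | 38.7 to 40.9 | 41.5 to 42.1 |
| 30 v 60 | 72.5 to 76.4 | 77.5 to 77.6 | 74.0 to 74.4 | 75.3 to 75.4 |
| 50 v 75 | 55.9 to 63.8 | 60.3 to 62.4 | 62.5 to 64.8 | 58.8 to 63.2 |

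At 40/40 the gains run from 76.4 - 72.5 = 3.9 to 63.8 - 55.9 = 7.9 points. At the unequal splits, the four main scenarios (50 v 25, 60 v 30, 40 v 15 and 30 v 10, higher rate in the larger arm) gain 0.1-4.9 points. Other pairs or orientations can go a little higher, for example 63.9 - 57.6 = 6.3 at 43/37.

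**6. Two concrete tables at 40/40.** 20 v 11 events gives pF = 0.066, and 13 v 5 gives pF = 0.059. Both exceed 0.05, so Fisher's test does not reject. Both are below 0.0707, so Boschloo's test does.

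**The case against.** The strongest reply is that nothing here is wrong. Fisher's test is standard, valid and pre-specified identically in both documents. Protocol Section 7 calls all analyses exploratory, the sample size has no power target, there is no multiplicity adjustment, and no stated decision depends on this p-value. All of that stands, and it limits the point to an efficiency suggestion.

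The size of the gain also depends on balance. Exactly equal arms are the unfavourable case for Fisher's test, and neither the PEA set nor the PPS need be balanced. If 8 of 44/44 patients were lost at random, 40/40 would result only about 29% of the time: C(44,4)² / C(88,8) = 0.287. At 60% v 30% the gain at the unequal splits examined is 0.5 points or less.

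A reader might go on to say that power is lost for nothing. That is too strong. Fisher's test guarantees the 5% ceiling, and two familiar alternatives do not: at 40/40 the maximum size is 5.9% for the uncorrected chi-square test and 5.7% for mid-p. The loss is avoidable only against an exact unconditional test. This part of the reply does not count against Boschloo's test, which keeps the ceiling.

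**Conclusion.** The point holds as a modest, optional improvement. Fisher's test is conservative here: about 2.8-3.3% at exactly 40/40 and about 3.4-4.75% at slightly unequal splits, for common event rates of 20-80%. Boschloo's test never loses power against it, and gains about 4-8 points at 40/40 and usually about 0-5 at slightly unequal splits. These figures rest on assumed event rates and on arm sizes near 40.

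Four stronger readings are not supported:

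- **That the test contradicts the SAP's level.** The 5% is an upper limit, and a valid test below it is consistent with SAP Section 4.
- **That the size is as low as 0.4%.** This needs exact balance and a composite rate near 5% or 95%. No rate is given. A composite that counts unchanged functional class, taken at its worst visit, is unlikely to be that rare; this is an inference.
- **That Fisher's test needs 47 per arm to match Boschloo's at 40.** This is true at 50% v 25% only with exact balance: 63.9% at 47/47 against 63.8% at 40/40. With the same 80 patients split 41/39, and the 50% rate in the arm of 41, Fisher's test already has 62.5%.
- **That this is the main clinical secondary endpoint.** It is the second of six listed, and the documents do not rank them.

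**What to change.** In SAP 8.2.2, state that the proportion of patients with a composite event is compared between arms by Boschloo's exact unconditional test, two-sided at 5%, using the two-sided Fisher p-value as the statistic and maximising over the common event rate. Name it as the designated test, with Fisher's p-value as a supportive line, so that the choice between them cannot follow the data. The functional-class test is unaffected.

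Because Protocol 7.8.2 also names Fisher's test, add the change to the list in SAP Section 11, before database lock and unblinding.

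The cost is one SAP sentence, one line in Section 11, slightly more computing and a test that is less familiar to readers. No new data are needed, and type I error control is kept.
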